# **Tracking Screened Subjects**

Local study sites will manage the tracking of all participants approached for the study, and will document who completed screening, who was ineligible (including reasons for exclusion), and who refused. An aggregated report of the screening outcome will be sent to Columbia University for the biweekly operations meetings.

#### **Tracking Enrolled Participants**

Tracking of enrolled participants will be managed through the web-based tracking system using a 'to-do-list' mechanism. When a participant comes in window for a follow-up visit, his/her ID number will appear in the 'to-do list' section of the study personnel's page on the tracking system. All contacts and communication attempts with the participant, including study payments, will also be logged in the tracking system.

#### **Data Discrepancies and Resolutions**

Data discrepancies and missing data reports from baseline, follow-up visit, and treatment-related information will be generated either (1) automatically by the webbased tracking system, or (2) by running program code(s) created by the data manager. The data manager will send a list of errors and detailed descriptions to the project managers for resolution. All sites are required to address all items in the report by checking available documentations to correct any inconsistency, or by declaring the item as permanently missing. The local sites' study personnel will be responsible for updating and correcting the data entry in the web-based system within two weeks of receipt of the report.

The data manager, will work with the study statistician and health economist, to check all variables from the EMR data extraction for outliers, consistency and completeness. A detailed report will then be sent to the site project managers to resolve any data inconsistencies and discrepancies. Resolutions to data queries from EMR data will be expected at the soonest possible time.

#### **Statistical Methods**

All analyses will use the principle of intention-to-treat. Baseline characteristics will be examined as means (standard deviation) or percentages by randomization assignment to confirm a balanced allocation. As randomization will be performed stratified by study site, we will also assess baseline characteristics further stratified by study site. Also, participant characteristics will be compared across study site

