# **Assignment of Interventions**

#### Sequence generation

Participants will be randomly assigned to one of three groups: No Depression Screen, Depression Screen and Notify, or AHA Depression Screen, Notify and Treat. The randomization algorithm will be embedded in the web-based tracking system, using randomly assigned block sizes of 3, 6 and 9.

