# **Hypothesis 1:**

Those randomized to AHA's Depression Screen, Notify & Treat intervention group will gain significantly more quality-adjusted life years across 18 months when compared to No Depression Screen control group, and also when compared to the Depression Screen & Notify control group.

We will compare outcomes for participants randomized to each of the three groups. Change in QALYs from baseline through 18 months post-randomization will serve as the primary outcome for this trial. First, quality of life utilities will be calculated using participants' scores on the SF-12 at each visit (baseline [pre-randomization] and 6, 12,

and 18 months post-randomization). All participants who complete the SF-12 will be classified according to the SF-6D. The SF-6D describes 18,000 health states. The average profile for each randomized group will be calculated. A multiple regression formula that applies weights will be used to assign quality of life utilities for each participant. Next, QALYs will be derived by multiplying the SF-6D derived quality of life utilities by 0.5 years for each 6 month-period, assuming linearity for changes in utility within each period. Any mortality events will be assigned zero QALYs from that point to the end of follow-up. With these scores calculated, we will calculate the average QALY gained (or lost) in each randomized group compared to assuming the utility calculated at baseline remained constant across 18-months.

The goal of the primary analysis is to identify whether there is difference in QALYs among the three groups. We plan to perform a two-step gate-keeping test procedure: We will first perform an F-test using ANOVA, and then proceed to do all three pairwise comparisons using two-sided t-test at 5% nominal significance *only if* the F-test has a p-value less than 0.05. With three randomization groups and three pairwise comparisons, this two-step procedure has been shown to preserve the familywise error rate in the strong sense, that is, a false positive comparison will occur at most with 5% probability under all possible scenarios.  This method is also generally more powerful than Bonferroni's adjustments.

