In a secondary analysis, we will use a mixed model with a random intercept to assess the change in quality of life utilities over time comparing individuals in the AHA Screen, Notify & Treat group vs. the other two randomization groups. This model will incorporate main effects of time (i.e., baseline, and 6-, 12-, and 18-months post-randomization), treatment group, and the time by treatment group interaction. Using this model, we will be able to calculate the mean utility at each follow-up time period for the 3 groups and determine whether the response profile differs by time across groups.

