3. RANDOMIZATION AND BLINDING

Sequence generation

Participants will be randomly assigned to one of three groups: No Depression Screen, Depression Screen and Notify, or AHA Depression Screen, Notify and Treat. The randomization algorithm will be embedded in the web-based tracking system, using randomly assigned block sizes of 3, 6 and 9.

Concealment Mechanism

Participants will be randomized using the web-based tracking system. "User-roles" are assigned to study personnel, and the randomization tool is only available to unblinded coordinators at each site. Concealment will be ensured as the randomization algorithm will run in the backend, and only the randomization assignment will be visible to the unblinded coordinator after all necessary information about the participant has been entered.

Implementation

All eligible participants who give consent will be randomized by the unblinded coordinator after completion of all baseline assessments. The randomization tool is only available to designated unblinded coordinators (UC) at each site. The UC will enter the required information in the tracking system, after which the participant's group assignment will be immediately available.

If the participant is randomized to the No Depression Screen arm, the UC will inform the participant that no further assessments are required.

If the participant is randomized to the Depression Screen and Notify arm, the UC will administer the PHQ-8. If the PHQ score is ≥ 10, the UC will notify the participant's primary care provider and/or cardiologist either through the tracking system, by email, or mail in accordance with their IRB requirements.

If the participant is randomized to the AHA Depression Screen, Notify, and Treat arm, the UC will administer the PHQ-8. IF the PHQ score is ≥ 10, the UC will inform the patient of the available treatment options. Depending on the participant's choice of treatment, the UC will facilitate the initial contact with the relevant treatment specialist(s), ideally within two weeks of randomization and will work closely with the treatment specialist(s) to monitor the participant's treatment progress. The participant's PCP and/or cardiologist will also be notified of the positive depression screen.

Blinding

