To determine the significance of differences, we will perform a two-step gate-keeping test procedure. This will involve first performing an F-test using ANOVA, and then proceeding to do all three pairwise comparisons using two-sided t-test at 5% nominal significance *only if* the F-test has a p-value less than 0.05. With three randomization groups and three pairwise comparisons, this two-step procedure can be shown to preserve the familywise error rate in the strong sense, that is, a false positive comparison will occur at most with 5% probability under all possible scenarios._{3,4} This method is also generally more powerful than Bonferroni's adjustments.

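### Randomisation is stated to be stratified by site, but the primary F-test and t-tests omit site; if so, they are at most slightly conservative, and a site term is nearly free

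*Protocol*

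**What the plan says.** Stratification by site is stated once, in the protocol's Statistical Methods section, where it justifies baseline tables: "As randomization will be performed stratified by study site".

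The sequence-generation text names no stratum. The protocol has "The randomization algorithm will be embedded in the web-based tracking system, using randomly assigned block sizes of 3, 6 and 9", and SAP section 3 repeats "using randomly assigned block sizes of 3, 6 and 9".

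The primary analysis names no factor other than arm. The protocol, under Hypothesis 1, has "We will first perform an F-test using ANOVA, and then proceed to do all three pairwise comparisons using two-sided t-test at 5% nominal significance", with the t-tests run only if the F-test gives p below 0.05. SAP 5.3 describes the same procedure: "This will involve first performing an F-test using ANOVA". The protocol's secondary mixed model has no site term either: "This model will incorporate main effects of time (i.e., baseline, and 6-, 12-, and 18-months post-randomization), treatment group, and the time by treatment group interaction".

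Site appears in three other places, none of which adjusts the primary test:
- SAP 5.6 gives site as an example of an imputation covariate.
- The protocol's Sensitivity Analysis section plans cost-effectiveness ratios separately by health system.
- The protocol plans baseline characteristics by site, while SAP section 6 mentions them by arm only.

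**The concern.** When allocation is blocked within site, the arms are balanced within each site. Differences between sites then add nothing to the sampling variation of the difference between arms. An analysis without site still counts those differences as residual error, so its standard error is larger than the true one. The F-gate and the pairwise tests then reject less often than their nominal 5%, and confidence intervals are wider than they need be.

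The sites could plausibly differ. Two are integrated health plans. One is a primary-care network that stopped recruiting in June 2015. One is an urban academic centre added in July 2016 to broaden ethnic diversity, and the only one enrolling Spanish speakers. Planned pairwise power is 80%, so there is little to give away, and no pairwise test is run unless the F-gate is passed.

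**Working it through.** **Inputs from SAP 5.4 and the protocol's Sample Size section:** SD 0.17, difference 0.031, two-sided 5%, 475 per group, 80% pairwise power, 84% F-test power, 5% loss. There are four health systems. **Assumption:** R², the share of variance in change in QALYs explained by site, is not given in the documents; I use 1%, 2%, 5% and 10%.

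**Step 1: the plan's own figures.**
- n per group = 2(1.96 + 0.842)² × 0.17² / 0.031² = 473, against the stated 475.
- Pairwise power at 475 is 80.2%.
- F-test power with one group above the other two is 82.5% (475 per group, effect size 0.18), 83.5% (475, effect size 0.031/0.17 = 0.1824) or 84.5% (500, 0.18), against the stated 84%.
- 475/0.95 = 500.

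The sample size reproduces.

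**Step 2: omitting site under site-stratified blocks.** The true SE is √(1−R²) times the SE that the unadjusted test uses. Hence:
- SE overstatement = 1/√(1−R²) − 1
- pairwise alpha = 2[1 − Φ(1.96/√(1−R²))]
- F-gate alpha = P(χ² on 2 df > 5.99/(1−R²))
- SE used by the unadjusted test: s = 0.17 × √(2/475) = 0.01103
- pairwise power without site = Φ[(0.031 − 1.96s)/(s√(1−R²))]
- pairwise power with site = Φ[0.031/(s√(1−R²)) − 1.96]

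The power figures are for one pairwise test, ignoring the gate.

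| Assumed R² | SE too large by | Pairwise alpha | F-gate alpha | Power without site | Power with site | Gain (points) |
|---|---|---|---|---|---|---|
| 0 | 0 | 5.0% | 5.0% | 80.2% | 80.2% | 0 |
| 1% | 0.5% | 4.9% | 4.9% | 80.4% | 80.6% | 0.3 |
| 2% | 1.0% | 4.8% | 4.7% | 80.5% | 81.0% | 0.5 |
| 5% | 2.6% | 4.4% | 4.3% | 80.9% | 82.2% | 1.4 |
| 10% | 5.4% | 3.9% | 3.6% | 81.5% | 84.2% | 2.7 |

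Power without site also rises with R², because within-site balance already makes the unadjusted estimate less variable. What remains to be gained is the correction of its SE.

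**Step 3: simulation under the null.** Settings: 1425 participants, four sites of assumed sizes 570, 570, 72 and 213, permuted blocks of 9, 8000 runs per setting, Monte Carlo SE about 0.24 points.
- Blocks within site, F-test/t-test rejection: 5.1%/5.0% at R² = 1%, 4.3%/4.8% at 5%, 3.4%/3.6% at 10%.
- Blocks ignoring site: all between 4.8% and 5.3%.

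The conservatism is therefore undetectable at 1%, seen in the F-test at 5%, and clear in both tests at 10%. It is absent if the blocks were not stratified.

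**Step 4: what the assumed R² implies.** The patient-weighted SD of the site mean changes is √R² × 0.17: 0.017 at 1%, 0.024 at 2%, 0.038 at 5% and 0.054 at 10%. The last two exceed the planned treatment difference of 0.031, and the last is close to the whole assumed background gain of 0.055.

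**The case against.** The strongest objection is that the effect may be close to nothing. SAP 5.3 subtracts from each participant's QALYs what would have accrued had the baseline utility stayed constant, which removes stable differences in level between sites. The listed site differences concern case mix, and nothing in the documents shows that they lead to different 18-month changes. Step 4 shows that the upper half of the range needs large site differences in change. This stands, and it pulls the likely effect towards the first rows of the table. It does not show that R² is zero, and it is no reason to leave the stratification factor out.

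Four stronger readings are tempting, and the documents do not support them:
- **The two documents contradict each other on stratification.** They do not. The sequence-generation sections are silent on strata, and Statistical Methods supplies the factor. This is missing detail.
- **The tests are conservative whatever was done.** That holds only if allocation was stratified and site predicts the outcome. With unstratified blocks, alpha stays near 5%.
- **Without stratification, chance site imbalance goes uncorrected.** Such imbalance is ordinary sampling variation, and the unadjusted SE already covers it. A site term would then bring precision, not a rescue.
- **The SAP withdraws the by-site baseline check.** SAP section 6 does not mention it, but the protocol still plans it, and it has no bearing on the primary test.

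The change also touches the primary model after recruitment is recorded as complete, so its timing has to be documented.

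**Conclusion.** The point holds in a limited, conditional form. If allocation was stratified by site as the protocol states, and site explains some of the variance of change in QALYs, the planned primary tests report standard errors that are slightly too wide. At an assumed R² of 1% to 2% the cost is 0.3 to 0.5 points of pairwise power, at 10% it is 2.7 points, and at zero there is none. The likely value is towards the low end.

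A reader might infer that the primary test is invalid or the trial underpowered. Neither follows: any error is on the safe side, and 475 per group reproduces. The case for acting is that the analysis would match the stated randomisation at almost no cost.

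**What to change.** In the protocol under Hypothesis 1 and in SAP 5.3, replace the ANOVA on arm alone with a linear model for change in QALYs with arm and site as fixed effects. Keep the 2-df F-test for arm at 0.05 as the gate, and take the three pairwise arm contrasts from the same model at two-sided 5%. The two-step logic is unchanged. Fit the model in each of the five imputed datasets and pool as SAP 5.3 already provides. For consistency, add site to the secondary mixed model.

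As housekeeping, confirm from the tracking system how allocation was generated and record it in the protocol's sequence-generation section and SAP section 3, naming site as the stratum if that is what was done. SAP section 6 can carry over the by-site baseline table that the protocol already plans.

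The cost is three degrees of freedom (four sites less one) out of about 1425 (3 × 475). Site is already recorded and already named for imputation. It needs a documented, dated update to both the SAP and the protocol, by whichever route the protocol's section on amendments requires, made before any unblinded analysis.

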# **Hypothesis 1:**

Those randomized to AHA's Depression Screen, Notify & Treat intervention group will gain significantly more quality-adjusted life years across 18 months when compared to No Depression Screen control group, and also when compared to the Depression Screen & Notify control group.

We will compare outcomes for participants randomized to each of the three groups. Change in QALYs from baseline through 18 months post-randomization will serve as the primary outcome for this trial. First, quality of life utilities will be calculated using participants' scores on the SF-12 at each visit (baseline [pre-randomization] and 6, 12,

and 18 months post-randomization). All participants who complete the SF-12 will be classified according to the SF-6D. The SF-6D describes 18,000 health states. The average profile for each randomized group will be calculated. A multiple regression formula that applies weights will be used to assign quality of life utilities for each participant. Next, QALYs will be derived by multiplying the SF-6D derived quality of life utilities by 0.5 years for each 6 month-period, assuming linearity for changes in utility within each period. Any mortality events will be assigned zero QALYs from that point to the end of follow-up. With these scores calculated, we will calculate the average QALY gained (or lost) in each randomized group compared to assuming the utility calculated at baseline remained constant across 18-months.

The goal of the primary analysis is to identify whether there is difference in QALYs among the three groups. We plan to perform a two-step gate-keeping test procedure: We will first perform an F-test using ANOVA, and then proceed to do all three pairwise comparisons using two-sided t-test at 5% nominal significance *only if* the F-test has a p-value less than 0.05. With three randomization groups and three pairwise comparisons, this two-step procedure has been shown to preserve the familywise error rate in the strong sense, that is, a false positive comparison will occur at most with 5% probability under all possible scenarios.  This method is also generally more powerful than Bonferroni's adjustments.

In a secondary analysis, we will use a mixed model with a random intercept to assess the change in quality of life utilities over time comparing individuals in the AHA Screen, Notify & Treat group vs. the other two randomization groups. This model will incorporate main effects of time (i.e., baseline, and 6-, 12-, and 18-months post-randomization), treatment group, and the time by treatment group interaction. Using this model, we will be able to calculate the mean utility at each follow-up time period for the 3 groups and determine whether the response profile differs by time across groups.

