5.4 Sample Size Determination

The sample size of the trial was determined based on an assumed standard deviation for QALYs of 0.17.5 Additionally, based on a general health-related quality of life outcome in a prior study of management of depression for patients with cancer, we assumed a net improvement in QALYs of 0.155 over 18 months of follow-up for depressed individuals who receive depression treatment in the Screen, Notify and Treat group.6 We assumed a 0.055 gain in QALYs for all patients not directly linked to depression treatment (i.e., those in the No Screen group, the Screen & Notify group and those without elevated depressive symptoms in the Screen, Notify, and Treat group). An important consideration for this trial is that only 20% of patients randomized to the Screen. Notify and Treat group were expected to meet criteria for elevated depressive symptoms and thus, to receive depression treatment. Therefore, assuming an increase in QALYs of 0.21 (0.055 background improvement + net improvement of 0.155) over the 18-month follow-up period for the 20% of patients diagnosed and treated for depression in the Screen, Notify, and Treat group and a 0.055 improvement in QALYs for the 80% of patients in this randomization group without depression, an overall gain in QALYs of 0.086 over the 18 month follow-up period was anticipated in this randomization group (0.21 * 0.2 + 0.055 * 0.8 = 0.086). Thus, we anticipated a difference in QALYs of 0.031 (0.086 change in the Screen. Notify, and Treat group minus 0.055 in the No Screen group or Screen and Notify Group), leading to an expected effect size of 0.18 (= 0.031/0.17). With this effect size, we determined the sample size per group to be 475, which would yield 80% power for a two-sided t-test at 5% level. We chose to determine sample size based on a pairwise comparison at 80% power in the two-step procedure (described above), as a conservative approach relative to powering based on the F-test. Specifically, under the scenario where one group has higher QALY than the other two by an effect size 0.18, the F-test will yield 84% power. Adding in 5% loss to follow-up, we selected an overall sample size of n=500 in each randomization group for an overall sample size of n=1500.

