8. SECONDARY EFFICACY ANALYSES

Key secondary outcomes included depression-free days and health care costs.

Depression-Free Days

The prespecified secondary outcome will be cumulative depression-free days based on the 10-item Center for Epidemiologic Studies Depression (CESD-10) scale, a non-diagnostic, epidemiologic, reliable and valid measurement for depressive symptoms, measured at baseline, 6-months, 12-months, and 18-months in all 3 arms. *Depression-free days* will be calculated by using linear interpolation to estimate daily depression severity at each of the four assessment time points for the 3 study arms. Depression-free days is a valid and easily interpretable measure for estimating depression treatment outcomes when multiple measures of depressive symptoms occur over time. This measure is also amenable to cost-effectiveness analyses. In other trials, Depression-free days have been calculated using intervals as long as 6 months. While a shorter interval (e.g., 3 months) can provide a more precise assessment of cumulative depressive symptoms over time, a 6-month interval was selected so as to avoid frequent

communication between the study team and study participants. More frequent assessments could lead to increased behavioral support and could cloud the interpretation of the No Depression Screen group which was not intended to receive any behavioral interventions.

An epidemiologic instrument was chosen over a clinical measure of depressive symptoms as the use of a clinical measure would have mandated referral for depression treatment in those who screened positive in the No Screen group. The CESD-10 is a short version of the original 20-item scale. The scores range from 0 to 30. A score 4 or greater has been found to be the optimal cutpoint for a positive depression screen with a sensitivity and specificity of 97% and 84%, respectively, compared to a psychiatric interview in a sample of older adults. Based on a review of the literature, we inferred that a cutpoint of 10 on the 10-item CESD would represent clinically significant depressive symptoms. 10

The following rule will be used to convert CESD score to depression day

CESD < 4 -> 0 depression day

CESD = 4 -> 1/7 depression day

CESD = 5 -> 2/7 depression day

CESD = 6 -> 3/7 depression day

CESD = 7 -> 4/7 depression day

CESD = 8 -> 5/7 depression day

CESD = 9 -> 6/7 depression day

CESD >= 10 -> 1 depression day

Health Care Costs and Lost Productivity

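### The protocol's secondary mixed model of utilities relies on a random intercept alone, which can misstate standard errors for change from baseline, and the SAP does not mention the analysis.

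*Protocol*

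**What the plan says.** In the protocol (Statistical Methods, Hypothesis 1) the model is labelled as a secondary analysis: "we will use a mixed model with a random intercept to assess the change in quality of life utilities over time", these being the SF-6D utilities. Its terms are "main effects of time (i.e., baseline, and 6-, 12-, and 18-months post-randomization), treatment group, and the time by treatment group interaction". It has two uses: to give the mean utility per group at each follow-up visit, and to "determine whether the response profile differs by time across groups". Neither document states a random slope, a residual covariance structure, robust standard errors or a sensitivity analysis on the covariance.

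The primary analysis is separate. SAP 5.3 reduces each patient to one change-in-QALY value and tests it in two steps: "This will involve first performing an F-test using ANOVA, and then proceeding to do all three pairwise comparisons using two-sided t-test at 5% nominal significance", the second step only if the F-test is significant.

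SAP section 8 opens with "Key secondary outcomes included depression-free days and health care costs" and then covers only depression-free days and costs with lost productivity. No repeated-measures analysis of utilities appears anywhere in the SAP. The summary of changes at the front of the protocol records no removal.

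**The concern.** With a random intercept and independent residuals, the correlation between baseline and 6 months is forced to equal that between baseline and 18 months, and all four visits share one variance. The fitted model then reports the same standard error for the arm difference in change from baseline at 6, 12 and 18 months, whatever the data show. If the true correlation declines with time, that common value is an average. It is too cautious for the nearest visit and too optimistic for the later ones.

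The model's purpose is to compare response profiles over time, and contrasts between visits are the quantities that depend on this covariance. At stake is a change-from-baseline difference at 12 or 18 months reported with a confidence interval that is too narrow, or a 6-month one reported with an interval that is too wide. In addition, because the SAP is silent, both whether the model is run and how it is specified remain open to choice after the data are seen.

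**Working it through.** **The plan's own figures first.** SAP 5.4 states that "we determined the sample size per group to be 475, which would yield 80% power for a two-sided t-test at 5% level". With a difference of 0.031 and an SD of 0.17, n = 2 × (1.960 + 0.842)² × (0.17/0.031)² = 473 per group. Power at 475 is 80.2%, and 475/0.95 = 500. The F-test power is 82.5% to 83.5% at 475 per group and 84.5% to 85.5% at 500, against the stated 84%; in each pair the lower value uses the rounded effect size 0.18 and the higher uses 0.031/0.17. These figures reproduce, and none of them uses the mixed model.

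**Inputs for the mixed model.** From the protocol: four visits, time and group as categories with their interaction, random intercept only. Assumed: complete data, equal variance σ² at each visit, and correlations c1, c2, c3 at lags of 6, 12 and 18 months. The documents give no correlation, so a range is shown.

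**Formulas.** With n patients per arm, for the arm difference in change from baseline to a visit at lag k:

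- True variance: 4σ²(1 − ck)/n.
- Variance reported by the random-intercept model: 4σ²(1 − r)/n, where r = (3c1 + 2c2 + c3)/6 is the mean of the six pairwise correlations.
- SE ratio (model/true) = √[(1 − r)/(1 − ck)].
- True type I error of a nominal 5% test = 2[1 − Φ(1.96 × ratio)].

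**Worked example, 0.7/0.6/0.5.** r = (2.1 + 1.2 + 0.5)/6 = 0.633. At 6 months the ratio is √(0.367/0.3) = 1.106, so the error is 3.0%. At 12 months it is √(0.367/0.4) = 0.957, giving 6.1%. At 18 months it is √(0.367/0.5) = 0.856, giving 9.3%.

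| Lag correlations | r | 6 months: ratio, error | 12 months: ratio, error | 18 months: ratio, error | Time-by-group F-test |
|---|---|---|---|---|---|
| Constant 0.7 | 0.700 | 1.00, 5.0% | 1.00, 5.0% | 1.00, 5.0% | 5.0% |
| 0.7/0.65/0.6 | 0.667 | 1.05, 3.9% | 0.98, 5.6% | 0.91, 7.4% | 5.2% |
| 0.6/0.5/0.4 | 0.533 | 1.08, 3.4% | 0.97, 5.8% | 0.88, 8.4% | 5.4% |
| 0.7/0.6/0.5 | 0.633 | 1.11, 3.0% | 0.96, 6.1% | 0.86, 9.3% | 5.7% |
| AR(1) 0.7 (0.7/0.49/0.343) | 0.571 | 1.20, 1.9% | 0.92, 7.2% | 0.81, 11.3% | 6.7% |

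The last column comes from simulating the interaction F-test at 475 per arm with no true difference.

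**Check by fitting.** A random-intercept model fitted to simulated AR(1) 0.7 data (475 per arm) gave an SE of 0.00720 at both 6 and 18 months, against true values of 0.00603 and 0.00893. The ratios, 1.19 and 0.81, agree with the formula.

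**A mechanism within the plan.** SAP 5.3 sets utility to 0 at assessments after death. If those zeros enter this model, they accumulate over visits, so variance grows and correlation with baseline falls even when survivors' correlation is constant. For illustration, assume survivors have a mean utility of 0.75, an SD of 0.12 to 0.15 and constant correlation 0.65, with deaths accruing evenly. Cumulative mortality of 1.5% at 18 months gives an 18-month type I error of 7.2% to 8.0%, and 3% mortality gives 8.5% to 9.5%. None of these inputs is in the documents, and neither document says whether the zeros enter the mixed model.

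**The case against.** The strongest reply is that the larger figures belong to contrasts that the protocol does not name as its test. Its two stated outputs are visit means and a comparison of profiles. The profile comparison is most naturally the overall interaction test, which stays within 5.2% to 5.7% under the gradual-decay patterns. An arm difference at one visit depends on the variance at that visit and not on between-visit correlation, so it is little affected if variances are equal. Both observations are correct and limit the point to change-from-baseline contrasts and, mildly, to the interaction test.

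A reader might also infer that the fault strikes the most important visit. The documents do not support that: nothing ranks 18 months above the others, and the primary outcome is an area under the curve over all four assessments.

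Nor do they support saying that the SAP dropped the model. The SAP is silent and states no removal. It is not exhaustive either: it repeats the cost-effectiveness hypothesis but gives no method for the incremental ratio. Its section 8 lists key secondary outcomes, whereas this model is a further analysis of the utilities behind the primary outcome. If the model was in fact abandoned, its covariance structure no longer matters. What remains in either case is that the two documents leave its status unclear.

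Finally, the decay in correlation is assumed. That stands, and so the result is conditional.

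**Conclusion.** The point holds in a limited form and is minor. As written, the random-intercept model cannot give different standard errors for change from baseline at 6, 12 and 18 months. If correlation falls with time, it is conservative at 6 months (3.0% to 3.9% for a nominal 5% test) and anti-conservative at 12 months (5.6% to 6.1%) and 18 months (7.4% to 9.3%), for lag correlations from 0.7/0.65/0.6 to 0.7/0.6/0.5. Faster decay makes it worse: 11.3% at 18 months under AR(1) 0.7. The interaction test is only mildly inflated, at 5.2% to 5.7%, or 6.7% under AR(1) 0.7. With constant correlation and variance there is no error. All of these figures assume complete data, equal variances and no robust standard errors.

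It would be wrong to infer that the trial's main conclusion is at risk. The ANOVA and t-tests use one value per patient, and the sample size rests on that comparison alone. Independently of any assumption about correlation, the protocol promises an analysis that the SAP does not carry.

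**What to change.** Carry the analysis into SAP section 8 as a repeated-measures model of utilities with visit, arm and visit-by-arm terms. Replace the random intercept alone with an unstructured covariance over the four visits, or keep it and use robust standard errors. An unstructured matrix for four visits has ten parameters (four variances and six covariances), easily estimated with about 1500 patients. Name the contrasts to be reported, and state whether utilities after death enter as zeros or are left out. If the analysis is no longer intended, record its removal in both documents with a reason.

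The cost is a paragraph of SAP wording. Data, visits, sample size and software stay the same.
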